### B. Evaluation during sirolimus treatment

Adverse reactions are evaluated weekly during the first month of drug treatment. The efficacy and safety are then evaluated at the 3rd and 6th months, and the contents of the examination is the same as the pre-trial evaluation.

1) Efficacy assessment:

a. Clinical symptom assessment (including ileus, VAS pain score, gastrointestinal bleeding and some other related symptoms);

b. Changes in hemoglobin;

c. Nutritional status (including albumin, etc.);

d. Abdominal and pelvic cavity contrast-enhanced CT + small intestine reconstruction CT examination, digestive system endoscopy to measure the size, quantity and total load of intestinal polyps;

e. (For patients with secondary malignant tumor) Tumor response to the drug, such as changes of tumor marker, tumor regression shown by imaging, metastasis and etc.

2) Safety assessment: Safety parameters (such as asking adverse events, measuring laboratory values, vital signs, gastrointestinal bleeding, etc.) will be closely monitored on a regular basis throughout the study.

3) Treatment compliance: In order to monitor compliance, subjects are required to complete an electronic diary during the entire study period. Dates of drug intake will be tracked by this diary. At every visit, the investigator and the subject will review the integrity of the electronic diary data together.

#### **C.** Evaluation after treatment

Evaluation of curative effects and safety is conducted at the end of the drug therapy, six and twelve months after the treatment. Its content is the same as pre-trial evaluation.

### VII. Records and reports of adverse events

### A. Adverse events

The term of adverse events encompass any signs, symptoms, syndromes or diseases affecting health condition of subjects during the trial. The term also includes clinically relevant conditions found by laboratory test or other diagnostic procedures. It may call for unplanned

treatment, or lead to withdrawal from the trial. Adverse events may be: new disease; deterioration of symptoms accompanying disease progression during treatment; certain events not related to the trial; combination of one or more events above.

#### Serious adverse events

At any dose of the test drug or at any time during the observation period, the following adverse events occurs: death; immediate life-threatening events; requirement of hospitalization or prolonged hospital stay; disability; congenital malformations; other events with important medical implications (those do not immediately endanger life or cause death or require hospitalization, but may harm the patient or require interventions to prevent one of the consequences defined above) and requiring medical treatment to prevent permanent injury.

#### **B.** Adverse reactions

Harmful and unexpected reactions caused by pharmaceutical applications under normal use of drugs and prescribed doses.

### C. Degree of adverse reactions:

- 1) Mild: causing mild discomfort which can be tolerated and does not affect daily life; under this circumstance, the subject does not need to discontinue medication.
- 2) Moderate: causing discomfort which affects patients' daily life.
- 3) Severe: affecting daily life; cannot be endured by the subject or cause organ damage and need to withdraw medication.
- 4) Very serious: risk of disability or death; require emergent rescue and drug withdrawal.

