### I. Background

Peutz-Jeghers syndrome (PJS) is an autosomal dominant hereditary syndrome, characterized by multiple hamartomatous polyps in gastrointestinal tract, pigmentation in skin mucosa and increased risk of cancer. PJS is a rare disease, with 1 patient in every 8000 to 200,000 births. Large intestinal polyps of PJS patients may lead to local necrosis, hemorrhage, intussusception and intestinal obstruction. The risk of lifelong occurrence of cancer among PJS patients is as high as 64%, with colorectal cancer being the most common one. Average age of cancer diagnosis in PJS patients is 41. At present, there is only invasive treatment for PJS, such as endoscopic polypectomy and surgery, without any drug treatment for choice. Endoscopic polypectomy applies to polyps over 0.5 cm in diameter. However, intestinal segmental resection is required when the polyps are too numerous, or progress into cancer, in which case endoscopic polyps control is infeasible. Invasive treatment exacerbates patients' suffering and increases risk of complications with high medical cost. It may also affect food digestion and absorption, even causing intestinal adhesions and shortbowel syndrome. Therefore, pharmaceutical intervention of PJS' underline pathogenesis is warrented.

The disease is most frequently caused by mutations in LKB1 which is detectable in 50-80% of the PJS family. LKB1 is a tumor suppressor gene. It encodes a serine/threonine kinase which activates the tumor suppressor genes TSC1 and TSC2 via stimulating adenosine 5'-monophosphate-activated protein kinase (AMPK). Activated TSC1-TSC2 complex inhibits the mammalian target of rapamycin (mTOR). Lkb1 deficiency causes PJS through activation of mTOR signaling. Therefore, mTOR inhibitor sirolimus (rapamycin) is a potential therapy for PJS.

Sirolimus is a macrolide antibiotics. It has been used to treat tuberous sclerosis complex, a benign tumor syndrome. The safety of rapamycin is widely recognized. The possible side effects are usually mild and may cause oral ulcers, hyperlipidemia, rash, acne and some other symptoms. While the efficacy of rapamycin on PJS has been demonstrated in mouse model, no clinical trial has been reported.

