#### C. Adults' dosage regimen

1) Initial dose and dosing schedule: sirolimus 2mg, once a day. Maintain drug trough concentration of 5-10ng / mL in blood. If adverse events are too severe to tolerate, daily dosage can be reduced by 0.5mg every week. The minimum dosage is 1 mg/day. If patient still cannot tolerate minimum dosage, withdraw from the study. If patient could tolerate the possible adverse events, continue to take the original dose for 3 months, and evaluate improvement of disease condition.

2) Subsequent dose and dosing schedule: After taking sirolimus 2 mg once a day for 3 months, those with improved condition continue to take the original dose. If improvement of disease condition is not obvious, change dosage to 2.5mg-3mg once a day. If this dosage cannot be tolerated, patients may withdraw from the study. If it can be tolerated, continue to take sirolimus for another 3 months and reassess the improvement of condition.

3) Blood drug concentration test: Blood samples are taken at 1st month, 3rd months, and 6th months of dosage schedules.

4) Iron supplementation: For subjects with hemoglobin  $\leq 10.9$  g / dl, iron supplementation should be provided according to the standard dosing regimen, but iron supplementation is not considered as study treatment and will be recorded as concomitant medication.

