### F. Treatment of adverse events

1) reporting system

Any adverse events, such as subjective discomfort and abnormal laboratory tests, should be taken seriously and carefully analyzed. Immediate measures should be taken to protect safety of the subject.

2) treatment procedure

Physicians are pre-trained to prevent certain types of adverse events or reactions that may occur in the study, so as to protect safety of patients. Treatment procedure of adverse event should be recorded in detail. Persistence and disappearance of adverse events should also be recorded.

3) treatment of serious adverse events

On the occurrence of any serious adverse event, research physician should report to primary PI within 24 hours, in addition to emergency treatment.

4) follow-up of unresolved adverse events

All adverse events should be tracked until they are properly resolved. Adverse events with abnormal laboratory values should be tracked until the value returns to baseline.

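### The severity scale has no laboratory criteria, so some symptom-free toxicity fits no grade, and its ambiguous link between Severe and drug withdrawal lets a dose-reduced intolerable event be graded either Moderate or Severe.

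*Combined protocol and SAP*

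**What the plan says.** Section VII.C defines four degrees:

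- Mild: "causing mild discomfort which can be tolerated and does not affect daily life", with no need to stop the drug.
- Moderate: "causing discomfort which affects patients' daily life".
- Severe: an effect on daily life, then "cannot be endured by the subject or cause organ damage and need to withdraw medication".
- Very serious: "risk of disability or death; require emergent rescue and drug withdrawal".

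The documents contain no other severity scale, and they cite no external toxicity criteria.

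The definition of an adverse event is wider than symptoms. Section VII.A states: "The term also includes clinically relevant conditions found by laboratory test or other diagnostic procedures". Section VII.F repeats the idea: "Any adverse events, such as subjective discomfort and abnormal laboratory tests, should be taken seriously and carefully analyzed". The Background says of sirolimus: "The possible side effects are usually mild and may cause oral ulcers, hyperlipidemia, rash, acne and some other symptoms". Section VI.A schedules liver, kidney and lipid tests before treatment, and section VI.B repeats the same examinations at months 3 and 6.

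For adults, section V.C says: "If adverse events are too severe to tolerate, daily dosage can be reduced by 0.5mg every week". On that initial schedule, withdrawal follows only if the lowest permitted dose is still not tolerated. Section VII.E has the investigator record the extent of each adverse event and the treatment measures taken.

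**The concern.** Safety is one of the trial's two objectives, and the plan counts laboratory abnormalities as adverse events. A scale whose two lower levels are both defined by discomfort may have no place for a finding the patient does not feel.

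The scale also mixes how bad an event is with what is done about it. Three of the four levels mention whether the drug must be stopped. Elsewhere the adult regimen treats an intolerable event first by lowering the dose. An event the protocol itself regards as intolerable might then miss Severe because it did not call for withdrawal.

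At stake is whether the recorded severity of adverse reactions means the same thing from one patient and one investigator to the next. The trial is open-label with a single arm, so no comparison group would show up inconsistent grading.

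**Working it through.** The plan states no figure on this point, so there is nothing to reproduce. The check applies the section VII.C definitions to five event profiles, then puts a scale on the result.

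**Readings of Severe.** The sentence joins its conditions with a semicolon, an *or* and an *and*. Three readings are tenable:

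- A: affects daily life AND (unendurable OR organ damage) AND need to stop the drug.
- B: (affects daily life AND unendurable) OR (organ damage AND need to stop the drug).
- C: (unendurable OR organ damage) AND need to stop the drug.

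Mild requires discomfort without effect on daily life. Moderate requires discomfort with such an effect. Very serious is not met by any profile below, since none is assumed to carry a risk of death or disability. Where the drug is continued or the dose reduced, withdrawal is taken as not judged necessary.

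| Event profile | A | B | C |
|---|---|---|---|
| 1. Symptom-free lipid rise | no grade | no grade | no grade |
| 2. Symptom-free organ damage on a laboratory test, drug continued | no grade | no grade | no grade |
| 3. As 2, drug needs to be stopped | no grade | Severe | Severe |
| 4. Intolerable event affecting daily life, dose reduced | Moderate | Severe | Moderate |
| 5. Intolerable event affecting daily life, drug needs to be stopped | Severe | Severe | Severe |

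Profiles 1 and 2 fit no level on any reading. Profile 3 depends on the reading. Profile 4 is the one that section V.C creates: Moderate on A and C, Severe on B. Very serious has the same shape (a criterion, then stopping the drug), which favours applying the need to stop to both alternatives, as A and C do. The text does not settle it.

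**Scale.** Section III sets a minimum of 10 patients, so one reclassified patient moves the severe-event rate by 1/10 = 10 percentage points. Section VIII.A asks for 95% intervals. The exact (Clopper-Pearson) limits for x of n = 10 are:

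- lower = 2.5% quantile of Beta(x, 11 − x), taken as 0 when x = 0;
- upper = 97.5% quantile of Beta(x + 1, 10 − x).

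For x = 0 the upper limit is 1 − 0.025^(1/10) = 0.3085.

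| Severe events | Rate | Exact 95% CI |
|---|---|---|
| 0/10 | 0% | 0% to 31% |
| 1/10 | 10% | 0.3% to 45% |
| 2/10 | 20% | 2.5% to 56% |
| 3/10 | 30% | 7% to 65% |

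The counts are assumed, because the documents give no expected number of intolerable events. If x adults have such an event and it settles after dose reduction, readings A and C record 0/10 where reading B records x/10. If reading B is the one used, nothing is lost.

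**The case against.** A reader might infer that the grades rest only on discomfort and on whether the drug was in fact stopped, so that all silent laboratory toxicity is ungraded and every dose-reduced event escapes Severe. The documents do not support that. Organ damage, effect on daily life, and risk of disability or death are also criteria. A large liver-enzyme rise judged to be organ damage that requires stopping the drug is Severe on two of the three readings. The text speaks of a need to stop the drug, which is a clinical judgement and not a record of what was done. The dose-reduction rule stands in the adult regimen only; section V.B, for children, has none. An adult who cannot tolerate even the lowest dose withdraws, and that event can then meet Severe.

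A reader might also infer that a planned severity table will be biased in the drug's favour. Sections VII.D and VII.E ask for the incidence of adverse reactions and adverse events, and section VIII.B asks for their assessment and relation to the drug. No severity distribution is explicitly planned, and grading does not change the incidence counts. An ungraded event is missing a grade, which is different from being graded too low.

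Laboratory values are also measured repeatedly, continuous variables are summarised, and section VII.F follows abnormal values until they return to baseline. A lipid rise would be seen even without a grade.

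All of this stands and narrows the point. None of it gives profiles 1 and 2 a grade, settles the scope of the withdrawal phrase, or separates severity from action. Extent is still a recorded item for each adverse event.

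**Conclusion.** The point holds in two parts.

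First, the scale cannot grade symptom-free laboratory abnormalities short of organ damage, with a lipid rise as the clearest case, or symptom-free organ damage when the drug is continued. This is true on every reading considered. It concerns a kind of event that the plan itself names and schedules tests for.

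Second, the tie between Severe and the need to stop the drug is ambiguous. On the reading that the wording of Very serious favours, an adult's intolerable event managed by dose reduction is only Moderate; on the other reading it is Severe. Two investigators could each follow the text and disagree.

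The size is 10 points on the severe-event rate per reclassified patient at the minimum enrolment, and zero if the second reading is used throughout. It rests on an assumed number of adults whose intolerable events settle after dose reduction. This should be corrected, but it does not affect the planned incidence of adverse events or adverse reactions.

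**What to change.** Keep the four levels and make three changes to section VII.C and the case report form:

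1. Add laboratory criteria to each level, taken from a published toxicity scale that covers lipids as well as liver and kidney tests. The multiples of the upper limit of normal in inclusion criterion 5 are not enough: they are eligibility limits for AST, ALT, bilirubin and creatinine, and they do not include lipids.
2. Define every level without reference to the action taken on the drug.
3. Record the action on study drug (none, reduced, stopped) as a coded item within the treatment measures that section VII.E already collects.

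The sponsor must also reconcile sections V.C and VII.C on intolerable events. No dose or management rule is proposed here.

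The cost is one revised table and one coded field. Recorded severity may look less favourable as a result.

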### D. Evaluation of the relationship between adverse reactions and experimental drug

According to the 5-level judgment system, the relationships can be divided into 5 types: definitely related, very likely related, may be related, may be irrelevant, and definitely irrelevant. The first three are counted as adverse reactions, in which case the incidence of adverse reactions and adverse events should be reported.

#### E. Record and report

The investigator should explain to the patient or his/her legal guardian that it is required to truthfully reflect the changes in the condition after administration. Doctors should avoid suggestive questions. While observing the efficacy, pay close attention to the observation of adverse events or unanticipated side effects (including symptoms, signs, laboratory tests), analyze the causes, make judgments, and report the incidence of adverse reactions and adverse events.

For adverse events occurring during the trial, time, symptoms, extent, duration, treatment measures, outcomes, and some other items should be recorded in the case report form to evaluate the correlation with the test drug. Investigator should record it in detail, and then signs and dates.

### F. Treatment of adverse events

1) reporting system

Any adverse events, such as subjective discomfort and abnormal laboratory tests, should be taken seriously and carefully analyzed. Immediate measures should be taken to protect safety of the subject.

2) treatment procedure

Physicians are pre-trained to prevent certain types of adverse events or reactions that may occur in the study, so as to protect safety of patients. Treatment procedure of adverse event should be recorded in detail. Persistence and disappearance of adverse events should also be recorded.

3) treatment of serious adverse events

On the occurrence of any serious adverse event, research physician should report to primary PI within 24 hours, in addition to emergency treatment.

4) follow-up of unresolved adverse events

All adverse events should be tracked until they are properly resolved. Adverse events with abnormal laboratory values should be tracked until the value returns to baseline.

### **VIII. Statistical analysis**

Statistical analysis will be conducted by SPSS.

#### A. Methods of statistical analysis

The categorical variables will be described by frequency distribution (number of cases and percentage). Continuous variables will be described with mean, median, minimum, maximum, first and third quartile. The confidence interval of all parameters is set to be 95%. All analyses will be conducted with SPSS.

### B. Contents of statistical analysis

1) General data analysis: Demographic variables and baseline characteristics will be summarized comprehensively by mean of descriptive statistics and/or appropriate frequency tables.

2) Evaluation of efficacy: According to follow-up and reexamination results, the patients' quality of life, size and volume of the polyps, total polyp load control and improvement of symptoms will be analyzed.

3) Analysis of adverse events: Side effects and adverse events during medication will be assessed.

4) Evaluation of the relationship between adverse events and the tested drug

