# III. Research design

- 1. This study is a prospective, nonrandomized, open-label, single-arm clinical trial. The sirolimus capsule (Rapamycin, Yixinke®), 0.5 mg/grain\*20/box, is produced by North China Pharmaceutical Co., Ltd.
- 2. All patients who meet inclusion criteria and sign informed consents receive sirolimus treatment for at least 6 months. Patients are followed up remotely in a regular schedule.
- 3. No less than 10 patients should be enrolled.

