# IV. Selection of subjects

### A. Inclusion criteria

- (1) Patients are diagnosed with PJS.
- (2) Patients have gastrointestinal polyps related syndromes, including abdominal pain, abdominal distension, gastrointestinal bleeding, etc, with imageological

examination suggesting intestinal obstruction or intussusception; or whose symptoms recur after previous digestive system endoscopic treatment and surgery; or who are inappropriate or unwilling to accept the above treatment again and wish to receive pharmacotherapy.

- (3) Conventional treatment doesn't work well in patients with PJS-related malignant tumors.
- (4) Physical condition (ECGO): 0~3
- (5) Organ function is good and biochemical indices meet the following conditions:
  - a) AST <2.5×upper limit of normal value (ULN),
  - b) ALT <2.5×upper limit of normal value (ULN),
  - c) Serum total bilirubin (TSB)≤1.5×upper limit of normal value (ULN),
  - d) Creatinine <1.5×upper limit of normal value (ULN).
- (6) No other medications have been received for intestinal polyps within 3 months prior to the clinical trial.
- (7) Patients volunteer to participate in the trial. Participant or his/her legal guardian signs the informed consent form.

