### C. Exit criteria

- (1) An allergic reaction occurs.
- (2) The patient requests withdrawal: at his or her own discretion or at the request of his or her legal representative. Subjects may refuse to participate in further studies at any time without providing reasons. Subjects will not be affected because of such decision.
- (3) Subjects are required to withdraw from the study in certain special circumstances. (eg, there is significant issues of compliance, safety, or surgery for venous malformations)
- (4) Other situations in which the study must be terminated. For example, the

investigators believe that continuing the study may be harmful to the health of subjects.

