### D. Rejection criteria

- (1) Patients who violate the requirements of the test protocol
- (2) Patients with poor-recording, incomplete, or inaccurate data

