## IX. Measures of quality control

1. Supervision by the project leader

2. Establish a standardized evaluation method, unify various diagnostic criteria and efficacy criteria

3. Formulate plans for monitoring and treatment of adverse reactions

4. All researchers are trained before the study begun

5. Designate quality controllers and develop a plan for quality control, with regular inspections

6. Devise a follow-up plan and system

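### The plan neither logs polyps removed after baseline nor says how they count, so a removal can look like a fall in polyp load on sirolimus

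*Combined protocol and SAP*

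**What the plan says.** The trial is a "prospective, nonrandomized, open-label, single-arm clinical trial" (section III), with a minimum size only: "No less than 10 patients should be enrolled". Polyp size, number and total load are measured by CT and endoscopy before treatment, at months 3 and 6, at the end of therapy, and again six and twelve months later (VI.A to VI.C). Section VIII.B then states, on the basis of follow-up and re-examination, that "size and volume of the polyps, total polyp load control and improvement of symptoms will be analyzed". Section VIII.A provides descriptive summaries, including the mean, median, quartiles and extremes, with 95% intervals.

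Four other places bear on removal:

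- Section I describes usual care: "Endoscopic polypectomy applies to polyps over 0.5 cm in diameter".
- Inclusion criterion IV.A(2) admits, among other routes joined by 'or', patients with signs of obstruction or intussusception on imaging and those "whose symptoms recur after previous digestive system endoscopic treatment and surgery".
- Exit criterion IV.C(3) gives as examples that "there is significant issues of compliance, safety, or surgery for venous malformations". Rejection criterion IV.D(2) covers "Patients with poor-recording, incomplete, or inaccurate data".
- Section IX promises to "Establish a standardized evaluation method, unify various diagnostic criteria and efficacy criteria", but the document states no such criteria.

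**The concern.** A polyp that has been cut out is no longer seen on the next CT or endoscopy. Measured number and load fall for a reason unrelated to sirolimus. With no control group, the data cannot show how much of an observed fall is due to removal.

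There are two separate problems, and they do not act on the same patient at once. In the first, the patient stays in the analysis and the removal lowers the measured load. In the second, the patient leaves for polyp surgery, is judged to have incomplete data and is rejected. A likely treatment failure is then lost from the denominator. Both outcomes favour the drug.

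The plan's analysis does not anticipate either. A removal may be known from the repeated medical history or from adverse event records. Neither source is required to hold the number and size of the polyps removed, which are needed to correct the load.

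**Working it through.** The plan gives no removal rate, effect size or sample-size derivation, so there is no figure to reproduce. The check has two parts.

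**1. Does any rule cover the gap?**

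| Place | What it covers | Covers removal after baseline? |
|---|---|---|
| IV.A(6) | Other polyp drugs in the 3 months before entry | No |
| IV.B(1), (2) | Surgery in the previous 2 weeks; likely emergency surgery, judged at entry | No |
| IV.C(3) | Open list of exit examples; the only surgery named is for venous malformations | Possibly as an exit, but with no analysis rule |
| IV.D(2) | Rejection for poor or incomplete data | May drop the patient |
| VI.B | Endoscopy as measurement | Neither plans nor forbids removal |
| VII.E | Treatment given for adverse events | Number and size not required |
| VIII.B, IX(2) | Polyp load analysed; efficacy criteria promised | No counting rule |

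The period at risk is at least 6 months of treatment (III) plus 12 months of follow-up (VI.C): 6 + 12 = about 18 months.

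**2. How much could a removal move the result?** (Illustration only.)

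Inputs: n = 10 is the minimum in section III. The number of patients with a removal, k, and the fraction of their load removed, f, are assumptions. The drug effect is set to zero.

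Shift in mean percentage change = −100 × k × f / n.

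| n | k | f = 0.25 | f = 0.50 | f = 0.80 |
|---|---|---|---|---|
| 10 | 0 | 0 | 0 | 0 |
| 10 | 1 | −2.5 | −5 | −8 |
| 10 | 2 | −5 | −10 | −16 |
| 20 | 1 | −1.25 | −2.5 | −4 |

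Median: with n = 10 and k = 1 or 2, at least eight patients have zero change. The fifth and sixth ordered values are both 0, so the median stays at 0. The minimum would show the affected patient.

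Chance of at least one removal among 10 patients, for an assumed per-patient probability p, is 1 − (1 − p)^10. For p = 5%, 10% and 20% this gives 40%, 65% and 89%.

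**Does the remedy work?** Take a baseline load of 20, with 10 removed and no drug effect.

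- Removed after the first dose, as measured: (10 − 20) / 20 = −50%. With add-back: (10 + 10 − 20) / 20 = 0%.
- Removed between baseline imaging and first dose, uncorrected: −50%. With the baseline corrected to 20 − 10 = 10: (10 − 10) / 10 = 0%.

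**The case against.** The strongest reply is that removal is not part of the trial. Study endoscopy is described only as measurement, likely emergency surgery is an exclusion, and some patients enter because they are unsuited to or do not want further procedures. The sentence on polypectomy in section I describes usual care, not trial conduct. All of this stands, and it means that the bias is possible rather than certain. It does not close the gap. Reluctance is only one of several entry routes, the emergency exclusion looks only to the near future, and nothing restricts removal over the 18 months.

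A reader might infer that section VIII.B scores a removed polyp as a response. It does not. It draws on follow-up as well as re-examination and states no scoring rule, so the supported statement is that the plan is silent.

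A reader might also expect an inflated response rate. The plan defines no responder and no threshold, so there is no such rate to inflate.

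The median would resist one or two affected patients out of 10, and the plan reports it. That limits the harm to the mean, but it does not protect individual patients' results or the denominator.

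Lastly, it is not certain that a patient who leaves with month-3 data counts as incomplete under IV.D(2). The wording permits that reading but does not require it.

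**Conclusion.** The omission is certain; the size of any bias is not. In a single-arm trial that can be as small as 10 patients, removals after baseline would either lower the measured load or, if the patient exits and is rejected, drop a likely failure. With no drug effect and one affected patient of 10, the mean change shifts by 2.5 to 8 percentage points if 25% to 80% of that patient's load is removed. With no removals the shift is 0. These figures rest on assumed inputs and show scale only.

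The naming of venous malformations in IV.C(3) is probably a drafting slip in an open list. It should not be read as proof that polyp surgery was meant to be allowed on study. Even if polyp surgery is an exit event, how that patient is analysed remains unstated. This should be fixed, because sizes that are not recorded at the time may not be recoverable later.

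**What to change.** 1. **Log.** At each scheduled visit, record the date, number, size and reason for every polyp removed since baseline imaging, taken from the procedure or pathology record.
2. **Load (VIII.B).** Report total load as measured and with removed polyps added back at their recorded size. Name the add-back version as the main one. Show both, because add-back freezes the removed polyp's size. Correct the baseline for polyps removed between imaging and first dose.
3. **Patients (VIII.B).** List separately those who need symptom-driven polypectomy or polyp surgery. Do not count them as improved from that date, however improvement comes to be defined. Keep them in the efficacy analysis using data already collected, regardless of IV.D(2).
4. **Exit criteria (IV.C(3)).** Replace venous malformations with PJS polyps.

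The cost is a short log, short amendment wording and some effort in matching removed polyps to records, which is harder when polyps are many or bowel has been resected. The reason for removal is an unblinded judgement. The apparent polyp reduction may be smaller. The fix does not require withdrawn patients to have further CT or endoscopy; asking for that would be an added cost.

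### The only stated window for the adverse-event analysis closes at the last dose, although safety is evaluated for 12 months afterwards

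*Combined protocol and SAP*

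**What the plan says.** Section VIII.B of the combined protocol and SAP lists four analyses. Item 3 covers harms: "Side effects and adverse events during medication will be assessed". Item 4, on the relationship of events to the drug, gives no window. Item 2 bases efficacy on follow-up and re-examination results and does not restrict them to time on drug.

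Other sections set longer periods:

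- **Visits (VI.C):** "Evaluation of curative effects and safety is conducted at the end of the drug therapy, six and twelve months after the treatment".
- **Definition of an adverse event (VII.A):** "any signs, symptoms, syndromes or diseases affecting health condition of subjects during the trial".
- **Serious adverse events (section VII):** "At any dose of the test drug or at any time during the observation period".
- **Recording and reporting (VII.D, VII.E):** events in the course of the trial go into the case report form, and incidence is to be reported. No on-drug limit is given.
- **Unresolved events (VII.F, item 4):** tracked until they resolve, which may be after the last dose.

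The design section says that patients "receive sirolimus treatment for at least 6 months" and that "No less than 10 patients should be enrolled".

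**The concern.** Evaluation of safety is one of the two objectives in section II. The plan brings patients back for safety evaluation at two visits off drug, but the section that says what will be analysed stops at the end of dosing. An analyst who works from section VIII would leave out any adverse event with onset after the last dose. One who works from section VII would include it. Both could claim to have followed the document, and they could report different incidences.

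Efficacy is not restricted in the same way. Polyp and symptom results from the post-treatment visits can enter the efficacy analysis under item 2, while new harms found at those same visits have no place under item 3. In a trial that may have as few as 10 patients, one event in or out moves a reported incidence by 1/10, or 10 percentage points.

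**Working it through.** The plan states no figure for safety follow-up, error rate or expected events, so there is nothing of its own to reproduce. The check is a comparison of windows, followed by simple arithmetic on size.

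**1. Windows side by side**

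| Purpose | Section | Window |
|---|---|---|
| Analysis of adverse events | VIII.B, item 3 | time on drug |
| Relationship to drug | VIII.B, item 4 | none stated |
| Analysis of efficacy | VIII.B, item 2 | follow-up results, no on-drug limit |
| Safety visits | VI.C | end of therapy, then 6 and 12 months later |
| Definition of adverse event | VII.A | the trial |
| Definition of serious event | VII, serious adverse events | the observation period |
| Recording | VII.E | the trial |
| Incidence reporting | VII.D, VII.E | no on-drug limit |

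Item 3 is the only analysis rule for adverse events that carries a window, and it is narrower than the windows for definition, recording and visits. The documents define neither a treatment-emergent event nor a lag after the last dose.

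VI.B also says that safety parameters "will be closely monitored on a regular basis throughout the study". That sentence sits under the heading for evaluation on treatment, so I give it little weight.

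**2. Share of scheduled observation outside the window**

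Inputs: T months on drug (minimum 6, section III) and 12 months of follow-up after treatment (VI.C).

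Share = 12 / (T + 12)

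- T = 6 (plan minimum): 12/18 = 67%
- T = 9 (assumed): 12/21 = 57%
- T = 12 (assumed): 12/24 = 50%

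For a patient who completes the minimum treatment, 67% is therefore the upper end. It measures calendar time, not the number of events.

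**3. Could this matter with 10 patients?**

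The documents give no risk of a new adverse event after treatment, so I assume a range. The chance of at least one patient with such an event is 1 − (1 − p)^10:

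- p = 5%: 1 − 0.95^10 = 40%
- p = 10%: 1 − 0.90^10 = 65%
- p = 20%: 1 − 0.80^10 = 89%

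These are illustrations. They show that the two windows could give different results even at modest risks.

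**The case against.** **The documents do not exclude later events.** Item 3 does not say that only on-drug events count. VII.D and VII.E ask for incidence without an on-drug limit, and item 4 has no window. This stands. A reader might infer that the post-treatment visits contribute nothing to safety, but the text does not go that far. It gives conflicting windows, with the narrow one in the statistical section, and they need to be reconciled.

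**Early stopping.** A reader might also infer that follow-up ends at the last dose for patients who stop because of toxicity, so that the loss is greatest in those who tolerated the drug worst. The documents do not support this. VI.C counts its visits from the end of drug therapy and does not require six months to have been completed. VII.F tracks every event to resolution. The event that leads to stopping begins on drug, so item 3 includes it. V.C has adults who cannot tolerate the lowest dose leave the study, and it does not say whether they attend later visits. That is an open question about data collection, not a consequence of the wording in VIII.B.

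**Some later harms are caught elsewhere.** VI.B lists ileus and gastrointestinal bleeding among the efficacy symptoms, so item 2 may pick them up after treatment. This also stands. The clear exposure is to new-onset events that are not already efficacy symptoms.

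**An on-treatment window is a recognised choice, and the trial is small and descriptive.** Both are true, and individual events could simply be listed. But the plan does not present the window as a deliberate choice and specifies no companion summary for the period off drug.

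**Conclusion.** The concern holds as a mismatch of windows. Taken as written, item 3 leaves adverse events with onset after the last dose outside the only stated safety analysis window, although the plan defines such events as adverse events, records them and schedules visits that would find them. At the minimum treatment duration this affects 12 of 18 months (67%) of scheduled observation, and 50% to 57% for an assumed 12 to 9 months on drug. These shares rest on reading VI.C as visits at the end of therapy and again 6 and 12 months later, with patients attending to month 12. The number of events affected cannot be derived from the documents.

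No sample size, error rate or efficacy result depends on the point. It should still be corrected before analysis, because safety is a stated objective and the present text permits two different incidences.

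**What to change.** Replace VIII.B, item 3, with:

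> All adverse events from first dose to the last follow-up visit will be summarised, separately for the on-treatment and post-treatment periods, in every patient who took at least one dose.

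This brings the analysis into line with VI.C and section VII, and keeps the on-drug summary as one of two columns. The sponsor should state where the boundary between the two periods lies, including any lag after the last dose. Naming the denominator also helps because section VIII defines no safety population and IV.D allows patients to be rejected for protocol violations or incomplete data.

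The cost is a change of wording and one more table. The data are already scheduled for patients who remain in follow-up. For those who leave the study early, the documents do not establish that post-treatment data will exist, so the table should show how many patients were observed in each period.
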